8.2 Procedures for Adverse Events

Treatment of an adverse event will depend on its nature and severity. Based on the clinical judgment of the investigator the subject may be referred to an ophthalmologist for treatment. The investigator will attempt to determine whether the reaction is related to the test device or a result of other factors. An Adverse Event Form will be completed for each adverse event. If both eyes are involved, a separate Adverse Event Form will be completed *for each eye*. Whenever possible, the adverse event will be photo-documented.

Expenses incurred for medical treatment as part of study participation will be paid by the sponsor (bills and prescription receipts kept). The subject must be followed until resolution and a written report completed indicating the subsequent treatment and resolution of the condition.

8.3 Reporting Adverse Events

All potential Serious and Unanticipated Adverse Device Effects that are related or possibly related to subject participation will be reported to the Principal Investigator and the sponsor within 24 hours of the investigator becoming aware of the event. The Principal Investigator will report the event to

the IRB as soon as possible (by fax, mail/delivery, phone, or email). All fatal or life threatening events will be reported immediately to the IRB.

Significant and Non-Significant Adverse Events will be reported to the sponsor as soon as possible, but no later than 5 working days after the occurrence.

Sponsor contact details are:

[REDACTED]

8.4 Discontinuation from the Study

A subject's study participation may be discontinued at any time if, in the opinion of the sponsor or the investigator it is in the best interest of the subject. All discontinuations will be fully documented on the appropriate study forms and the Discontinuation Form will be completed.

9 Device Malfunctions

A device malfunction means the failure of the device to meet its performance specification or otherwise perform as intended. *Any defective lens that is likely to cause or contribute to a Serious Adverse Event should be reported to the Principal Investigator and the sponsor **within 24 hours** of the investigator becoming aware of the malfunction.*

Other defective lenses should be reported to the Sponsor as soon as possible.

[REDACTED]

10 Statistical Analysis

10.1 Statistical analysis

Summary statistics will be produced (e.g. mean, standard deviation). Paired t test will be used to compare slit lamp biomicroscopy, [REDACTED]. Repeated Measures Analysis of Variance (ANOVA) or paired analysis will be used to compare the variables between study visits. The critical alpha level for statistical significance will be set at $p \leq 0.05$, with adjustment for multiple comparisons. Non-inferiory or equivalence testing will be conducted as appropriate.

All participants who were evaluated will be used in the analysis. In the event of missing data, individual data points will be excluded in the analysis and not extrapolated from the collected data.

11 Data Quality Assurance

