CooperVision is evaluating the clinical performance of its Phoebe contact lenses (Test) compared to the commercially available MyDay contact lenses (Control) over 3-day of lens wear on a daily wear, daily disposable modality in a randomized, double masked, bilateral, cross-over dispensing study.

2 Study Objective

The purpose of this study is to validate the clinical performance of the Phoebe contact lenses.

The primary variable of interest is:

- Anterior ocular health examination

The secondary variable of interest is:

- Visual acuity and Vision quality

[REDACTED]

- [REDACTED]
- [REDACTED]
- [REDACTED]

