2.1 Study Hypotheses

The primary study hypothesis is that the Phoebe contact lens performs substantially equivalent to the MyDay contact lens for ocular health.

The secondary study hypothesis is that The Phoebe contact lens is not inferior to the MyDay contact lens for vision and visual acuity.

[REDACTED]

- [REDACTED]
- [REDACTED]

[REDACTED]

3 Study Design

This will be a double-masked, randomized, bilateral, cross-over, 3-day dispensing study comparing the Phoebe Test lens against the MyDay Control lens. Each subject will be randomized to wear either the Test or Control lenses first as a matched pair. Each lens pair will be worn for 3 days. All lenses will be replaced daily.

It is anticipated that this study will involve up to 4 scheduled visits:

- Visit 0: Enrolment / Screening / Baseline Visit
- Visit 1: Dispensing of Pair 1
- Visit 2: Follow-up of Pair 1 (+2 days) and Dispensing of Pair 2
- Visit 3: Follow-up of Pair 2 (+2 days) and Exit

4 Ethics Review / Statement of Compliance

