7.2 Participants

Up to 80 subjects will be recruited for this study with the goal to have approximately 50 subjects to complete in total. Each subject will be given a unique ID number. Additionally, all subjects must meet the study inclusion and exclusion criteria listed below.

Inclusion criteria

A person is eligible for inclusion in the study if he/she:

- **Between and 18 and 35 years of age** and has full legal capacity to volunteer
- Has had a self-reported oculo-visual examination in the last two years
- Has read and understood the information consent letter
- Is willing and able to follow instructions and maintain the appointment schedule
- Is correctable to a visual acuity of 20/25 or better (in each eye) with their habitual correction or 20/20 best corrected
- Has a Contact Lens Refraction between -1.00D and -6.00D
- Cylinder power \leq **-0.75DC** in Spherical Cylindrical Refraction
- Currently wears soft contact lenses
- **Is willing to wear lenses for a minimal of 8 hours a day and everyday during the course of the study**
- Has clear corneas and no active ocular disease
- Has not worn lenses for at least 12 hours before the first visit

Exclusion Criteria

A person will be excluded from the study if he/she:

- Has never worn contact lenses before
- Is wearing Monovision modality
- Has any systemic disease affecting ocular health
- Is using any systemic or topical medications that will affect ocular health
- Has any ocular pathology or severe insufficiency of lacrimal secretion (moderate to severe dry eyes) that would affect the wearing of contact lenses
- Has persistent, clinically significant corneal or conjunctival staining using sodium fluorescein dye
- Has any clinically significant lid or conjunctival abnormalities, active neovascularization or any central corneal scars
- Is aphakic
- Has undergone corneal refractive surgery
- Is participating in any other type of eye related clinical or research study

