15. The subject will be given enough lenses including spares to last them until the next visit.

16. The subject will be discharged and scheduled to come back for the follow-up visit wearing the study lenses for at least two hours within the required visit window.

17. The subject will be instructed to come back for the follow-up visit wearing the study lenses for at least two hours prior to the visit time.

7.4.3 Visit 2: Follow up lens pair 1/Dispensing lens pair 2 (3 days +2 days from Visit 1)

Subjects should attend wearing the study lenses, which should have been in situ for at least two hours. Subjects who attend without lenses in situ for at least two hours will be rescheduled. The following procedures will be performed (any ocular measurement procedures outlined below will be carried out on each eye):

1. Average Wear Time; Wear Time at visit; Problems and Comments will be recorded.

2. Subjects will return any unworn lenses and problem lenses.

[REDACTED]

[REDACTED]

[REDACTED]

5. Visual Acuity will be assessed with the contact lenses.

a. Distance visual acuity

i. High Illumination High Contrast (OU)

ii. High Illumination Low Contrast (OD, OS, OU)

iii. Low Illumination High Contrast (OD, OS, OU)

- b. Near visual acuity
 - i. High Illumination High Contrast (OU)
 - ii. Low Illumination High Contrast (OU)

High Illumination: Overhead lights on, Ideal: 60cd/m², Range: 120-200cd/m²

Low Illumination: Overhead lights off, Ideal: Ideal: 3cd/m², Range: 1-5cd/m²

6. Monocular over-refraction and High Illumination High Contrast logMAR VA @ 4m (OU) will be performed and recorded.
7. [REDACTED]
8. Lens removal and lens storage.
9. Slit lamp biomicroscopy will be assessed set out in the CVI grading scales.
10. Eyes will be rinsed.
11. The Randomised Pair 2 lenses will be fitted.
12. Initial contact lens power chosen based on vertexed, spherical equivalent obtained from refraction (i.e. match the initial power of the first pair).
13. The initial lens fit will be assessed for fit acceptance (acceptable or not acceptable). If the fit is acceptable, the subject will be allowed to sit in the waiting area for a minimal of 10 minutes to allow for the lenses to settle.
14. Visual acuity with initial contact lens power will be assessed.
 - a. Distance visual acuity
 - i. High Illumination High Contrast (OU)
 - ii. Low Illumination High Contrast (OU)
 - b. Near visual acuity
 - i. High Illumination High Contrast (OU)
 - ii. Low Illumination High Contrast (OU)

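### Does naming a paired t test for slit-lamp findings leave the primary equivalence hypothesis without a valid test?

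*Combined protocol and SAP*

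**What the plan says.** Section 2 gives the primary variable as "Anterior ocular health examination". Section 2.1 states: "The primary study hypothesis is that the Phoebe contact lens performs substantially equivalent to the MyDay contact lens for ocular health". The secondary hypothesis there is that "The Phoebe contact lens is not inferior to the MyDay contact lens for vision and visual acuity". Redacted lines follow.

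Section 10.1 states "Paired t test will be used to compare slit lamp biomicroscopy", and a black-out begins directly after those words. It then allows repeated-measures ANOVA or a paired analysis between visits, sets significance at 0.05 with a multiplicity adjustment (method not named), and closes with a one-line provision for non-inferiority or equivalence tests where they apply.

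Section 7.2 gives the sample size: "Up to 80 subjects will be recruited for this study with the goal to have approximately 50 subjects to complete in total". At Visit 2 (section 7.4.3), and in the same terms at Visit 3 (section 7.4.4), "any ocular measurement procedures outlined below will be carried out on each eye". After lens removal at each of these visits, "Slit lamp biomicroscopy will be assessed set out in the CVI grading scales". The content of Appendix 2, which holds those scales, is redacted throughout.

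**The concern.** A t test of no difference and an equivalence claim pull in opposite directions. Fewer completers, noisier grading or a stricter alpha all make a non-significant t test easier to obtain and an equivalence criterion harder to meet. If the only test tied by name to slit-lamp data were read as the test of the primary hypothesis, imprecision would be rewarded, and the promised multiplicity adjustment would make that worse.

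The readable text also leaves choices open: which slit-lamp signs carry the claim, how right and left eyes enter the analysis, what margin applies, what counts as a pass, and which acuity score decides non-inferiority. Made after unmasking, such choices could favour the Test lens. Analysing two correlated eyes as independent would also understate the standard error. At stake would be the credibility of the primary conclusion.

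**Working it through.** The plan gives no power, SD, effect size or margin in readable text, so there is no stated figure to reproduce. From the plan: about 50 completers, two eyes per subject, alpha 0.05. Assumed for illustration: SD of the within-subject Test-Control difference of 0.5, 0.75 or 1.0 grade; margin of 0.25 or 0.5 grade; inter-eye correlation of 0.3 to 0.8.

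**1. Which test answers which hypothesis.** Section 2.1 assigns equivalence to ocular health and non-inferiority to vision. Section 10.1 provides for both kinds of test. Read together, the test type for each hypothesis follows. The paired t test is compatible with this: two one-sided tests (TOST) on a paired difference use the same mean, standard error and t distribution, with the null value moved from zero to the margin.

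**2. The misreading, if it were made.** With n = 50, the two-sided t test is non-significant when the observed mean difference is below t(0.975, 49)/√50 = 2.010/7.071 = 0.284 SD. When the true worsening equals the margin, the probability of non-significance comes from the noncentral t with noncentrality margin × √50 / SD. For example, 0.25 × 7.071/0.5 = 3.54. TOST passes when the observed mean plus or minus t(0.95, 49) × s/√50 (that is, 0.237 s, where s is the sample SD) stays inside the margin.

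| Margin = true worsening | SD | Noncentrality | t test non-significant | TOST passes |
|---|---|---|---|---|
| 0.25 | 0.5 | 3.54 | 7% | 5.0% |
| 0.25 | 0.75 | 2.36 | 36% | 4.9% |
| 0.25 | 1.0 | 1.77 | 59% | 2.2% |
| 0.5 | 0.5 | 7.07 | <0.1% | 5% |
| 0.5 | 0.75 | 4.71 | 0.4% | 5% |
| 0.5 | 1.0 | 3.54 | 6.6% | 5% |

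At the wider margin, the misreading is stricter than TOST in two of three cases and nearly equal in the third. The large figures belong to the tight margin with noisy grades.

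**3. Sample size.** TOST power at zero true difference, one sign, n = 50, is 93%, 50% and 10% at margin 0.25 and above 99.9%, 99.7% and 93% at margin 0.5 (SD 0.5, 0.75, 1.0). The documents do not show which applies, so no shortfall is demonstrated.

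**4. Two eyes.** If 100 eyes were treated as independent, a one-sided 5% test at the margin would have an error of about 1 − Φ(1.645/√(1 + ρ)), which is 7.5%, 9% and 11% at ρ = 0.3, 0.5 and 0.8. The plan does not say the eyes will be treated this way. One value per subject, or a model with a subject effect, is routine.

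**5. Choice of visit.** There is none for the primary variable. Each lens has one follow-up slit-lamp examination, after removal at Visit 2 or Visit 3.

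**6. Acuity.** At each follow-up, scores with the study lenses are 1 + 3 + 3 + 1 + 1 = 9, plus the binocular high-contrast acuity recorded with the over-refraction, making 10. Unadjusted free choice among ten independent scores, all truly at the margin, would give a false claim with probability 1 − 0.975^10 = 22.4% at one-sided 2.5%. Section 10.1 promises a multiplicity adjustment. A Bonferroni split of 2.5% over ten scores (0.25% each) holds the total at 2.5% or less.

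**The case for a change.** The strongest reply is that equivalence cannot be tested without a margin, and that a general provision naming no endpoint, margin or decision rule pre-specifies very little. That sentence is readable and unbroken, so redaction does not explain its vagueness. The adverse-event grades in section 8.1 are reporting thresholds and do not fill the gap. Writing down signs, eyes, margin and rule would take a few sentences, and a choice made after unmasking could not be repaired.

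Much of this stands as description. A reader of the public text cannot confirm that the margin and the deciding signs were fixed in advance, or that the multiplicity adjustment extends to the non-inferiority tests. What does not stand is the step from there to an error. The signs would naturally sit in the grading scales, and a margin could sit beside the hypotheses or in the rest of the t-test sentence. All three places are blacked out. The two-eye rule has the best claim to be missing from section 10.1 itself, but part of that section is hidden too, and any competent analyst would respect the pairing of eyes. No stated rule has been shown to give a wrong answer.

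**Conclusion.** No change to the plan is called for. The test type follows from sections 2.1 and 10.1 read together. What is left is unwritten or hidden detail that the analyst has to supply and can supply sensibly: deciding signs, one value or a model per subject, a margin, and a confidence interval judged against it.

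The size of any harm depends on inputs the documents do not give. At 50 completers, misreading non-significance as equivalence would pass a lens that is worse by exactly the margin between under 0.1% and 59% of the time over the assumed SDs and margins. Treating eyes as independent would raise a 5% error to 7.5–11%. Both figures require conduct that the plan never describes. Section 6 also says the two lenses share the same material and differ in optical design, which makes a sizeable ocular-health difference less likely, though it does not replace the test.

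The conclusion rests on reading the equivalence provision in section 10.1 as applying to the primary hypothesis, and on not counting redacted text as absent. It would change if results were reported with a non-significant paired t test as the evidence of equivalence.

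### The paired t test named for slit lamp ignores the randomised lens order, and no readable text says how the two eyes enter it

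*Combined protocol and SAP*

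**What the plan says.** Section 2 names "Anterior ocular health examination" as the primary variable, and section 2.1 sets the primary hypothesis that "the Phoebe contact lens performs substantially equivalent to the MyDay contact lens for ocular health". That slit lamp biomicroscopy measures this variable is a fair inference; the document does not say so in those words.

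Section 3 describes a two-period cross-over: "Each subject will be randomized to wear either the Test or Control lenses first as a matched pair".

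Sections 7.4.3 (Visit 2) and 7.4.4 (Visit 3) both state that "any ocular measurement procedures outlined below will be carried out on each eye". Slit lamp follows lens removal at each of these visits: "Slit lamp biomicroscopy will be assessed set out in the CVI grading scales". Some acuities are also recorded for each eye as well as binocularly, for example "High Illumination Low Contrast (OD, OS, OU)".

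Section 10.1 gives the analysis: "Paired t test will be used to compare slit lamp biomicroscopy", after which the sentence is redacted. It continues: "Repeated Measures Analysis of Variance (ANOVA) or paired analysis will be used to compare the variables between study visits". It adds that non-inferiority or equivalence testing will be done where appropriate, and that missing data points will be left out. Period, sequence and the handling of two eyes do not appear in its readable text.

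**The concern.** There are two gaps, both in the primary comparison.

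The first is period. Randomising lens order lets the analysis separate a lens effect from a visit effect. A plain paired t test on Test minus Control does not use the order. Any shift between the first and second wearing period goes into the variance of the differences. If unequal numbers complete the two orders, part of it also goes into the estimate.

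The second is the unit of analysis. Each lens yields two slit-lamp values per subject, and a paired t test needs a defined pair. The plan could mean the mean of two eyes, one chosen eye, the worse eye, or each eye as its own pair. The last, if the eyes are treated as independent, overstates the information. Because the aim is to show equivalence, an interval that is too narrow favours the conclusion sought. The rule on missing data points also leaves open what happens to a subject with one eye missing. Binocular acuities are not affected by this second gap.

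**Working it through.** **Inputs.** Section 7.2 gives a target of about 50 completers from up to 80 recruited. No readable text gives an SD, margin, correlation, period effect or power, so the 50 cannot be reproduced and is taken as given. Everything else below is assumed and shown as a range. The unit is the SD of the within-subject Test minus Control difference, and a normal model is used.

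**Period: formulas.** Let δ be the lens difference and p the shift from period 1 to period 2. The within-subject difference has mean δ − p if Test is worn first and δ + p if Control is worn first.

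- The paired estimate has expected value δ + p(n_C − n_T)/n, where n_C and n_T are the completers with Control first and Test first.
- The adjusted estimate is the mean of the two sequence means, and p cancels.

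**Period: balanced completion, 25:25.** There is no bias, but the SD used by the paired test is inflated to about √(1 + p²). Power for δ = 0.4 is then about Φ(0.4√50 − 2.01√(1 + p²)), with 0.4√50 = 2.828.

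| p | 2.01√(1+p²) | Power, paired (formula) | Power, paired (simulated) | Type I error, paired (simulated) |
|---|---|---|---|---|
| 0.25 | 2.072 | Φ(0.756) = 77.5% | 77% | 4.4% |
| 0.5 | 2.247 | Φ(0.581) = 71.9% | 72% | 2.8% |
| 1 | 2.843 | Φ(−0.015) = 49.4% | 49% | 0.6% |

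Adjusted power is about 79% whatever p is, and adjusted type I error is about 5%.

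**Period: unequal completion.** The bias is (28 − 22)/50 = 0.12p at 28:22 and (30 − 20)/50 = 0.20p at 30:20. At 30:20 the paired type I error is about 5.7%, 6.9% and 8.7% for p = 0.25, 0.5 and 1. At 28:22 it is 4.9%, 4.3% and 2.7%. The adjusted analysis stays at about 5% throughout.

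**Period: allocation method.** If allocation is balanced, the paired test is conservative. If each subject is allocated independently 1:1, simulated paired type I error is 5% at all three values of p, because chance imbalance offsets the inflated SD.

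**Eyes.** Suppose 100 eye differences are entered as independent, with between-eye correlation ρ of those differences. The true variance of the mean is (1 + ρ) times the variance assumed, so two-sided type I error is 2(1 − Φ(1.96/√(1 + ρ))).

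| ρ | 1.96/√(1+ρ) | Type I error | False equivalence at the margin (one-sided 5% test, simulated) |
|---|---|---|---|
| 0.3 | 1.719 | 8.6% | 7.4% |
| 0.5 | 1.600 | 11.0% | 9.0% |
| 0.7 | 1.503 | 13.3% | 10.4% |
| 0.9 | 1.422 | 15.5% (simulated, up to 15.9%) | 11.8% |

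The interval is about 13% to 29% narrower than the one from subject means. With one mean per subject, both error rates return to about 5%.

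**Price of adjusting when there is no period effect.** The expected width ratio is the ratio of t quantiles and expected SDs (48 against 49 degrees of freedom, about 1.0004) times √(n²/(4n₁n₂)). The second factor is 1 at 25:25, √(2500/2464) = 1.0073 at 28:22 and √(2500/2400) = 1.0206 at 30:20. The interval is wider by 0.04%, 0.8% and 2.1%.

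**The case against.** The strongest reply is that a paired t test in a randomised cross-over is not an error. That stands: it is unbiased on average. At a period effect of 0.25 SD the loss is about two points of power. Nothing in the document suggests a larger effect. Subjects already wear soft lenses, both lenses share material, base curve and diameter, and lenses are replaced daily. Adjustment is therefore the better method rather than the repair of an invalid one.

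A reader might go further and say how likely a harmful imbalance is. The document cannot support that. The randomisation table is redacted, and the chance of 28:22 or worse in one direction depends on the allocation method: it is 24% with 50 completers under independent 1:1 allocation, and lower under balanced allocation. For the same reason the paired test cannot be called conservative without qualification.

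A reader might infer that eyes will be treated as independent. No readable text says so. The inflated error rates are conditional on it, and they come from a normal model, whereas slit-lamp grades may be sparse and the grading scales are redacted.

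A reader might also infer from the wording on study visits that no lens comparison is planned for the other variables, or that Visit 2 against Visit 3 would serve as one. Neither is supported. Section 2.1 states the Test against Control hypothesis for vision and visual acuity. The list of variables under the paired t test is partly redacted. Acuity is measured with the same lens at dispensing and at follow-up, so comparing visits within a lens is an ordinary analysis. Nor does the phrase allowing repeated measures ANOVA exclude a period term for those variables.

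**Conclusion.** The point holds in limited form. For slit lamp, section 10.1 names a test that leaves the randomised order unused, and its readable text does not define the pair.

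The period part is a matter of precision, with bias only when completed orders are unequal. The loss runs from slight to large over the assumed range of 0.25 to 1 SD, and the document gives no basis for choosing within it. The eye part is conditional. It has no effect if eyes are combined within subject, and it produces a material excess of false equivalence claims if they are entered as independent pairs. Taken alone it is close to missing detail. It matters because the analyst would otherwise choose the unit for the primary comparison.

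The plan should be changed, but nothing here shows that it would give a wrong answer. All sizes assume 50 completers and normally distributed differences.

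**What to change.** In section 10.1, for slit lamp and the other readable follow-up outcomes, state the following.

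- **Unit.** Per-eye follow-up values are reduced to one value per subject per lens, the mean of the two eyes. For slit lamp the worse eye is a supporting summary, because the mean halves a finding present in one eye only. State the rule when one eye is missing.
- **Timing.** The value comes from that lens's own follow-up assessment: Pair 1 at Visit 2 before Pair 2 is fitted, and Pair 2 at Visit 3. This matters for acuity, because Visit 2 also holds Pair 2 dispensing values.
- **Model.** Test minus Control is estimated with lens, period and sequence as fixed effects and subject as random. For complete pairs this is the two-sequence period-adjusted t test. Its confidence interval is used for the equivalence and non-inferiority decisions.
- **Sparse grades.** Support the slit-lamp result with a rank-sum test of within-subject period differences between the two sequences.

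Keep dispensing-to-follow-up comparisons within a lens, comparisons with baseline, and exit against baseline acuity.

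The cost is wording, a standard model and one degree of freedom, with the small widening of the interval shown in the working. Visits and measurements do not change. The model does not remove carry-over.

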15. After lens settling a standard monocular over-refraction will be performed. The endpoint of this over refraction will be the best objective acuity and subjective acuity improvement.
 - c. Up to -0.50D will be given if objective visual acuity is improved.
 - d. -0.25D will be given if subjective visual acuity is significantly improved.
16. A lens change will be implemented if over-refraction dictates. The replacement lens will be allowed to settle for 10 minutes.
17. Change lens prescription to that noted by over-refraction, if needed.

18. Visual Acuity will be assessed with the final lens powers.

e. Distance visual acuity

- i. High Illumination High Contrast (OU)
- ii. High Illumination Low Contrast (OD, OS, OU)
- iii. Low Illumination High Contrast (OD, OS, OU)

f. Near visual acuity

- i. High Illumination High Contrast (OU)
- ii. Low Illumination High Contrast (OU)

High Illumination: Overhead lights on, Ideal: 60cd/m², Range: 120-200cd/m²

Low Illumination: Overhead lights off, Ideal: Ideal: 3cd/m², Range: 1-5cd/m²

[REDACTED]

[REDACTED]

21. The subject will be instructed to wear lenses for a minimal of 8 hours/day and every day until the subject come back for the follow-up visit.

22. The subject will be given enough lenses including spares to last them until the next visit.

23. The subject will be discharged and scheduled to come back for the follow-up visit wearing the study lenses for at least two hours within the required visit window.

24. The subject will be instructed to come back for the follow-up visit wearing the study lenses for at least two hours prior to the visit time.

7.4.4 Visit 3: Follow-up lens pair 2 and Exit (3 days +2 days from Visit 2)

Subjects should attend wearing the study lenses, which should have been in situ for at least two hours. Subjects who attend without lenses in situ for at least two hours will be rescheduled. The following procedures will be performed (any ocular measurement procedures outlined below will be carried out on each eye):

- 1. Average Wear Time; Wear Time at visit; Problems and Comments will be recorded.
- 2. Subjects will return any unworn lenses and problem lenses.

5. Visual Acuity will be assessed with the final lens powers.
 - a. Distance visual acuity
 - i. High Illumination High Contrast (OU)
 - ii. High Illumination Low Contrast (OD, OS, OU)
 - iii. Low Illumination High Contrast (OD, OS, OU)
 - b. Near visual acuity
 - i. High Illumination High Contrast (OU)

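### The paired t test for slit-lamp grades drops any subject stopped at Visit 2 with one graded period; if signs are uncommon and the lenses truly differ, this slightly favours equivalence

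*Combined protocol and SAP*

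**What the plan says.** Section 2 makes the anterior ocular health examination the primary variable. The primary hypothesis in 2.1 is that the Test lens "performs substantially equivalent to the MyDay contact lens for ocular health".

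In 7.4.3 (Visit 2), Pair 1 is removed at step 8 and the eyes are graded by slit lamp at step 9. At step 11, "The Randomised Pair 2 lenses will be fitted". The Pair 1 outcome is therefore recorded before any Pair 2 exposure. Section 8.4 lets the sponsor or the investigator withdraw a subject at any time in that subject's interest. Adverse event code 24 in 8.1 foresees signs that call for a lens stop of more than one day.

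Section 10.1 sets the analysis:
- For the slit lamp: "Paired t test will be used to compare slit lamp biomicroscopy" (the rest of that sentence is blacked out; I read it as comparing Test with Control).
- For comparisons across visits: "Repeated Measures Analysis of Variance (ANOVA) or paired analysis will be used to compare the variables between study visits".
- For the analysis set: "All participants who were evaluated will be used in the analysis".
- For gaps in the data, the rule is separate: "In the event of missing data, individual data points will be excluded in the analysis and not extrapolated from the collected data".

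On numbers, 7.2 says "Up to 80 subjects will be recruited for this study with the goal to have approximately 50 subjects to complete in total". The readable text gives no sign rate, stop rate, grade SD or equivalence margin.

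**The concern.** A paired t test works on within-subject differences. A subject stopped between steps 9 and 11 of Visit 2 has one grade and no difference, and so leaves the comparison. The missing-data rule does not prevent this: once the absent Pair 2 point is excluded, the paired test discards the Pair 1 point with it. Section 10.1 names no method that can keep its promise to use everyone evaluated.

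The loss is not random. The subjects removed are those in whom the first lens produced a sign. If the Test lens caused more signs than Control, more Test-first subjects would be removed, and the remaining pairs would understate the difference. In an equivalence trial, that error helps the claim being tested.

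**Working it through.** The plan states no power, SD or margin, so there is no figure to reproduce. Every rate below is an assumption.

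**1. Direction, two-level sign.** Let pT and pC be the shares of subjects with a sign on Test and on Control, p11 the share with a sign on both, and s the chance of being stopped after a Pair 1 sign. Assume equal sequences and no period effect.
- Test-first: the expected retained difference is pT − s·pT − pC + s·p11, and the share retained is 1 − s·pT.
- Control-first: the expected retained difference is pT − s·p11 − pC + s·pC, and the share retained is 1 − s·pC.
- In the sum p11 cancels, so within-subject correlation does not matter. The sum is (2 − s)(pT − pC), over a retained share of 2 − s(pT + pC).

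Complete-pairs estimate / true difference = (2 − s) / (2 − s(pT + pC)).

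This is below 1 exactly when pT + pC < 1. The expected number stopped of 50 is 50·s(pT + pC)/2.

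| pT, pC | s | ratio | stopped of 50 |
|---|---|---|---|
| 0.10, 0.02 | 0.1 | 1.9/1.988 = 0.956 | 0.3 |
| 0.10, 0.02 | 0.5 | 1.5/1.94 = 0.773 | 1.5 |
| 0.10, 0.02 | 1 | 1/1.88 = 0.532 | 3 |
| 0.20, 0.10 | 0.5 | 1.5/1.85 = 0.811 | 3.75 |
| 0.70, 0.50 | 1 | 1/0.80 = 1.25 | 30 |

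The last row shows why the condition that signs are uncommon is needed: with common signs the bias reverses. If pT = pC the numerator is zero, and if s = 0 the ratio is 1, so there is no bias in either case.

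**2. Size, graded outcome.** Slit-lamp findings are graded, so a 0-4 scale is closer to this trial. Assumed Control distribution: 60/30/8.5/1.4/0.1%. Test is shifted by 0.3 latent SD (48/36/13/2.8/0.3%). The true difference is 0.199, latent correlation 0.5, and 50 subjects start. The margin is set equal to the true difference, with a one-sided 5% bound, so any conclusion of equivalence is false. With 4,000 runs the Monte Carlo error is about 0.4 points. With no stops, false equivalence is 5.4%.

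| Stopped at Visit 2 | of 50 | Complete pairs: estimate (shrinkage), false equivalence | Mixed model: estimate (shrinkage), false equivalence |
|---|---|---|---|
| grade 3 or more | 1.2 | 0.185 (7%), 6.5% | 0.194 (2%), 5.9% |
| half of grade 2 or more | 3.3 | 0.184 (7%), 7.0% | 0.198 (under 1%), 5.5% |
| all of grade 2 or more | 6.6 | 0.164 (18%), 8.5% | 0.192 (4%), 6.4% |

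A repeat simulation on the same inputs gave shrinkage of 6%, 9% and 19% for complete pairs and about 1%, 3% and 5% for the mixed model. The second decimal should not be leaned on. With correlation 0 the complete-pairs estimates are 0.177, 0.178 and 0.153 (11%, 11% and 23%).

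In the first two rows the shift is 0.199 − 0.184 = 0.015 grade at most. Against an estimate SD of 0.118 this is 0.015/0.118 = 0.13, about one-eighth of a standard error.

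**3. Why the mixed model helps.** Here the stop depends on the observed Pair 1 grade. A likelihood-based model that keeps that grade allows for the loss, as far as its normal, constant-correlation form fits. The fit is not exact. On the two-level scale with latent correlation 0.5 the model is 3.5% low at s = 0.5 and 13% low at s = 1 (pT 0.10, pC 0.02). It is 5% and 19% low for 0.20 and 0.10. The complete-pairs ratios there are 0.773 and 0.532, then 0.811 and 0.588.

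**The case against.** The strongest reply is that the bias needs two things together: a true lens difference in ocular health, and sign-driven stops after Pair 1. The documents make both look uncommon. The lenses share material, base curve and diameter (7.3.1), and only the optical design differs (section 6). Subjects are current soft lens wearers with clear corneas, wearing each lens for about three days. The adverse event table also sets a high bar: staining becomes a significant event only at grade 3, so stopping everyone at grade 2 is not what 8.1 suggests. This stands, and it is why the size is put as small.

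It is also fair that 10.1 does not name the paired t test as the equivalence test, leaves the equivalence method open and gives no margin. The false-equivalence figures therefore illustrate a mechanism and do not predict this trial's error rate. The signs themselves are not lost: adverse event forms (8.2) and discontinuation forms (8.4) record them. They are missing only from the primary comparison.

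A reader might infer more than the documents support:
- *That up to 30 of 80 subjects are lost to signs.* Under 7.4.1 a subject counts as enrolled at consent, before eligibility is confirmed, so the gap between 80 and 50 includes screen failures and its split is not given.
- *That the true difference would be roughly halved.* That needs a two-level outcome with every sign leading to a stop.
- *That Visit 2 lacks a rule for withholding Pair 2.* Sections 8.2 and 8.4 leave this to clinical judgment, and Appendix 2 is blacked out and may hold a rule.
- *That the Visit 3 window is mistimed.* The heading of 7.4.3 defines Visit 2 as including Pair 2 dispensing, so a window counted from Visit 2 can be read as counted from dispensing.

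**Conclusion.** The point holds as an inconsistency in 10.1 with a known direction and a probably small effect. The named test cannot use a subject with one graded period, although the same section says everyone evaluated will be used. If signs are uncommon (shares on the two lenses summing to less than 1) and the lenses truly differ, the loss shrinks the difference and slightly favours the primary claim.

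Under the assumed 0-4 grades, shrinkage is about 7% (6 to 9% across runs) with 1 to 3 of 50 stopped, and 18 to 19% if every subject at grade 2 or more is stopped. These figures rest on assumed grade distributions, stop rules, correlation and margin, and on reading the partly blacked-out sentence as a Test-Control comparison. The documents do not show that the trial's conclusion would change. The change is worth making because it is cheap and makes 10.1 self-consistent.

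**What to change.** In 10.1, replace the paired t test for slit-lamp grades with a linear mixed model: lens and period as fixed effects, subject as a random effect, one value per subject and period. Use every graded period, including those of subjects with only one, and read equivalence from the confidence interval for lens. Nothing is imputed, so the missing-data sentence and the analysis-set sentence can both stay.

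Add two reporting items:
- The number of subjects stopped after Pair 1, by lens.
- A comparison of Pair 1 grades alone between sequences, as a sensitivity check. These grades precede any Visit 2 stop, so that loss cannot bias them.

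No change to the visit schedule or the Visit 2 procedures is proposed.

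The cost is one or two sentences in 10.1 and slightly more analysis work. The interval is a little wider because the high grades are kept: the estimate's SD is 0.123 against 0.118 with 3.3 of 50 stopped. The Pair 1-only check is imprecise (SD about 0.22, larger than the 0.199 difference assumed above), so it cannot carry the conclusion. Some bias remains if nearly every subject with a sign is stopped, which is why the stops by lens need to be shown.
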